## RENAL EVENTS

Immune-mediated nephritis has been associated with the administration of atezolizumab. Eligible patients must have adequate renal function. Renal function, including serum creatinine, should be monitored throughout study treatment. Patients with abnormal renal function should be evaluated and treated for other more common etiologies (including prerenal and postrenal causes, and concomitant medications such as non steroidal anti-inflammatory drugs). Refer the patient to a renal specialist if clinically indicated. A renal biopsy may be required to enable a definitive diagnosis and appropriate treatment.

Patients with signs and symptoms of nephritis, in the absence of an identified alternate etiology, should be treated according to the guidelines in Table 16.

**Table 16. Management Guidelines for Renal Events**

Event	Management
Renal event, Grade 1	

Continue atezolizumab

Monitor kidney function, including creatinine and urine protein, closely until values resolve to within normal limits or to baseline values.

Renal event, Grade 2	

Withhold atezolizumab for up to 12 weeks after event onset.a

Consider patient referral to renal specialist.

Initiate treatment with corticosteroids equivalent to 1-2 mg/kg/day oral prednisone.

If event resolves to Grade 1 or better, resume atezolizumab.b

If event does not resolve to Grade 1 or better while withholding atezolizumab, permanently discontinue atezolizumab and contact Sponsor-Investigator.c

Renal event, Grade 3 or 4	

Permanently discontinue atezolizumab and contact Sponsor-Investigator.c

Refer patient to renal specialist and consider renal biopsy.

Initiate treatment with corticosteroids equivalent to 1-2 mg/kg/day oral prednisone.

If event does not improve within 48 hours after initiating corticosteroids, consider adding an immunosuppressive agent.

If event resolves to Grade 1 or better, taper corticosteroids over <math>\geq</math> 1 month.

a Atezolizumab may be withheld for a longer period of time (i.e.,  $>$  12 weeks after event onset) to allow for corticosteroids (if initiated) to be reduced to the equivalent of  $\leq$  10 mg/day oral prednisone. The acceptable length of the extended period of time must be based on an assessment of benefit–risk by the investigator and in alignment with the protocol requirements for the duration of treatment and documented by the investigator.

b If corticosteroids have been initiated, they must be tapered over  $\geq$  1 month to the equivalent of  $\leq$  10 mg/day oral prednisone before atezolizumab can be resumed.

c Resumption of atezolizumab may be considered in patients who are deriving benefit and have fully recovered from the immune-related event. The decision to re-challenge patients with atezolizumab should be based on investigator's assessment of benefit–risk and documented by both the investigator (or an appropriate delegate) and the Sponsor-Investigator.

## HEPATIC EVENTS

Immune-mediated hepatitis has been associated with the administration of atezolizumab. Patients eligible for study treatment must have adequate liver function, as manifested by measurements of total bilirubin and hepatic transaminases, and liver function will be monitored throughout study treatment. Management guidelines for hepatic events are provided in [Error! Reference source not found.17](#).

Patients with right upper-quadrant abdominal pain and/or unexplained nausea or vomiting should have liver function tests (LFTs) performed immediately and reviewed before administration of the next dose of study drug.

For patients with elevated LFTs, concurrent medication, viral hepatitis, and toxic or neoplastic etiologies should be considered and addressed, as appropriate.

**Table 17. Management Guidelines for Hepatic Events**

Event	Management
Hepatic event, Grade 1	

Continue atezolizumab.

Monitor LFTs until values resolve to within normal limits or to baseline values.

Hepatic event, Grade 2	
All events:
 

Monitor LFTs more frequently until return to baseline values.

 
Events of > 5 days' duration:
 

Withhold atezolizumab for up to 12 weeks after event onset.a

Initiate treatment with corticosteroids equivalent to 1-2 mg/kg/day oral prednisone.

If event resolves to Grade 1 or better, resume atezolizumab.b

If event does not resolve to Grade 1 or better while withholding atezolizumab, permanently discontinue atezolizumab and contact Sponsor-Investigator.c

Hepatic event, Grade 3 or 4	

Permanently discontinue atezolizumab and contact Sponsor-Investigator.c

Consider patient referral to gastrointestinal specialist for evaluation and liver biopsy to establish etiology of hepatic injury.

Initiate treatment with corticosteroids equivalent to 1-2 mg/kg/day oral prednisone.

If event does not improve within 48 hours after initiating corticosteroids, consider adding an immunosuppressive agent.

 
If event resolves to Grade 1 or better, taper corticosteroids over <math>\geq</math> 1 month.

LFT = liver function test.

a Atezolizumab may be withheld for a longer period of time (i.e.,  $>$  12 weeks after event onset) to allow for corticosteroids (if initiated) to be reduced to the equivalent of  $\leq$  10 mg/day oral prednisone. The acceptable length of the extended period of time must be based on an assessment of benefit–risk by the investigator and in alignment with the protocol requirements for the duration of treatment and documented by the investigator.

b If corticosteroids have been initiated, they must be tapered over  $\geq$  1 month to the equivalent of  $\leq$  10 mg/day oral prednisone before atezolizumab can be resumed.

c Resumption of atezolizumab may be considered in patients who are deriving benefit and have fully recovered from the immune-related event. The decision to re-challenge patients with atezolizumab should be based on investigator's assessment of benefit–risk and documented by both the investigator (or an appropriate delegate) and the sponsor-investigator.

## IMMUNE-MEDIATED MYOSITIS

Immune-mediated myositis has been associated with the administration of atezolizumab. Myositis or inflammatory myopathies are a group of disorders sharing the common feature of inflammatory muscle injury; dermatomyositis and polymyositis are among the most common disorders. Initial diagnosis is based on clinical (muscle weakness, muscle pain, skin rash in dermatomyositis), biochemical (serum creatine kinase increase), and imaging (electromyography/MRI) features, and is confirmed with a muscle biopsy. Patients with possible myositis should be referred to a rheumatologist or neurologist. Patients with possible myositis should be monitored for signs of myocarditis.

Patients with signs and symptoms of myositis, in the absence of an identified alternate etiology, should be treated according to the guidelines in [Table 8](#).

**Table 18 Management Guidelines for Immune-Mediated Myositis**

Event	Management
Immune-mediated myositis, Grade 1	

Continue atezolizumab.

Refer patient to rheumatologist or neurologist.

Initiate treatment as per institutional guidelines.

Immune-mediated myositis, Grade 2	

Withhold atezolizumab for up to 12 weeks after event onset.a

Refer patient to rheumatologist or neurologist.

Initiate treatment as per institutional guidelines.

Consider treatment with corticosteroids equivalent to 1–2 mg/kg/day IV methylprednisolone and convert to 1–2 mg/kg/day oral prednisone or equivalent upon improvement.

If corticosteroids are initiated and event does not improve within 48 hours after initiating corticosteroids, consider adding an immunosuppressive agent.

If event resolves to Grade 1 or better, resume atezolizumab.b

If event does not resolve to Grade 1 or better while withholding atezolizumab, permanently discontinue atezolizumab.c

Immune-mediated myositis, Grade 3	

Withhold atezolizumab for up to 12 weeks after event onset.a

Refer patient to rheumatologist or neurologist.

Initiate treatment as per institutional guidelines.

Respiratory support may be required in more severe cases.

Initiate treatment with corticosteroids equivalent to 1–2 mg/kg/day IV methylprednisolone, or higher-dose bolus if patient is severely compromised (e.g., cardiac or respiratory symptoms, dysphagia, or weakness that severely limits mobility); convert to 1–2 mg/kg/day oral prednisone or equivalent upon improvement.

If event does not improve within 48 hours after initiating corticosteroids, consider adding an immunosuppressive agent.

If event resolves to Grade 1 or better, resume atezolizumab.b

If event does not resolve to Grade 1 or better while withholding atezolizumab, permanently discontinue atezolizumab.c

For recurrent events, treat as a Grade 4 event.

Immune-mediated myositis, Grade 4	

Permanently discontinue atezolizumab.c

Refer patient to rheumatologist or neurologist.

Initiate treatment as per institutional guidelines.

Respiratory support may be required in more severe cases.

Initiate treatment with corticosteroids equivalent to 1–2 mg/kg/day IV methylprednisolone, or higher-dose bolus if patient is severely compromised (e.g., cardiac or respiratory symptoms, dysphagia, or weakness that severely limits mobility); convert to 1–2 mg/kg/day oral prednisone or equivalent upon improvement.

If event does not improve within 48 hours after initiating corticosteroids, consider adding an immunosuppressive agent.

If event resolves to Grade 1 or better, taper corticosteroids over <math>\geq</math> 1 month.

a Atezolizumab may be withheld for a longer period of time (i.e.,  $>$  12 weeks after event onset) to allow for corticosteroids (if initiated) to be reduced to the equivalent of  $\leq$  10 mg/day oral prednisone. The acceptable length of the extended period of time must be based on an assessment of benefit–risk by the investigator and in alignment with the protocol requirements for the duration of treatment and documented by the investigator.

b If corticosteroids have been initiated, they must be tapered over  $\geq$  1 month to the equivalent of  $\leq$  10 mg/day oral prednisone before atezolizumab can be resumed.

c Resumption of atezolizumab may be considered in patients who are deriving benefit and have fully recovered from the immune-mediated event. The decision to re–challenge patients with atezolizumab should be based on investigator's assessment of benefit–risk and documented by the investigator (or an appropriate delegate).

## **HEMOPHAGOCYTIC LYMPHOHISTIOCYTOSIS AND MACROPHAGE ACTIVATION SYNDROME**

Immune-mediated reactions may involve any organ system and may lead to hemophagocytic lymphohistiocytosis (HLH) and macrophage activation syndrome (MAS), which are considered to be potential risks for atezolizumab.

Clinical and laboratory features of severe CRS overlap with HLH, and HLH should be considered when CRS presentation is atypical or prolonged.

Patients with suspected HLH should be diagnosed according to published criteria by McClain and Eckstein (88). A patient should be classified as having HLH if five of the following eight criteria are met:

- Fever  $\geq 38.5^{\circ}\text{C}$
- Splenomegaly
- Peripheral blood cytopenia consisting of at least two of the following:
  - Hemoglobin  $< 90 \text{ g/L}$  ( $9 \text{ g/dL}$ ) ( $< 100 \text{ g/L}$  [ $10 \text{ g/dL}$ ] for infants  $< 4$  weeks old)
  - Platelet count  $< 100 \times 10^9/\text{L}$  ( $100,000/\mu\text{L}$ )
  - ANC  $< 1.0 \times 10^9/\text{L}$  ( $1000/\mu\text{L}$ )
- Fasting triglycerides  $> 2.992 \text{ mmol/L}$  ( $265 \text{ mg/dL}$ ) and/or fibrinogen  $< 1.5 \text{ g/L}$  ( $150 \text{ mg/dL}$ )
- Hemophagocytosis in bone marrow, spleen, lymph node, or liver
- Low or absent natural killer cell activity
- Ferritin  $> 500 \text{ mg/L}$  ( $500 \text{ ng/mL}$ )
- Soluble interleukin 2 (IL-2) receptor (soluble CD25) elevated  $\geq 2$  standard deviations above age-adjusted laboratory-specific norms

Patients with suspected MAS should be diagnosed according to published criteria for systemic juvenile idiopathic arthritis by Ravelli et al. (89). A febrile patient should be classified as having MAS if the following criteria are met:

- Ferritin  $> 684 \text{ mg/L}$  ( $684 \text{ ng/mL}$ )
- At least two of the following:
  - Platelet count  $\leq 181 \times 10^9/\text{L}$  ( $181,000/\mu\text{L}$ )
  - AST  $\geq 48 \text{ U/L}$
  - Triglycerides  $> 1.761 \text{ mmol/L}$  ( $156 \text{ mg/dL}$ )
  - Fibrinogen  $\leq 3.6 \text{ g/L}$  ( $360 \text{ mg/dL}$ )

Patients with suspected HLH or MAS should be treated according to the guidelines in [Table 9](#).

**Table 19 Management Guidelines for Suspected Hemophagocytic Lymphohistiocytosis or Macrophage Activation Syndrome**

Event	Management
Suspected HLH or MAS	
 
• Permanently discontinue atezolizumab.
 
• Consider patient referral to hematologist.
 
• Initiate supportive care, including intensive care monitoring if indicated per institutional guidelines.
 
• Consider initiation of IV corticosteroids, an immunosuppressive agent, and/or anti-cytokine therapy.
 
• If event does not respond to treatment within 24 hours, initiate treatment as appropriate according to published guidelines (90-92).
 
• If event resolves to Grade 1 or better, taper corticosteroids over <math>\geq</math> 1 month.
 

HLH = hemophagocytic lymphohistiocytosis; MAS = macrophage activation syndrome.

## 6.2 Abemaciclib Toxicity Management

**Table 20. Diarrhea**

Diarrhea	Management
(management overview)	
Clinical trial data indicates the majority of patients who receive abemaciclib will develop diarrhea. Our experience indicates early identification and intervention for the management of diarrhea has been helpful to patients.
 
At time of enrollment, patients should receive instructions on the prompt management of diarrhea. In the event of diarrhea, supportive care measures should be initiated as early as possible. These include the following:
 
At the first sign of loose stools, the patient should initiate antidiarrheal therapy (e.g., loperamide) and notify the investigator for further instructions and appropriate follow-up.
 
Patients should also be encouraged to drink fluids (e.g., 8 to 10 glasses of clear liquids per day).
 
Site personnel should assess response within 24 hours.

Grade 1	Dose modification not required.
Grade 2	If toxicity does not resolve within 24 hours to $\leq$ Grade 1, suspend dose until resolution. Dose reduction not required.
Grade 2 that persists or recurs after resuming the same dose despite maximal supportive measures	Suspend dose until toxicity resolves to $\leq$ Grade 1. Resume at next lower dose.
Grade 3 or 4, or requiring hospitalization	

**Table 21. Interstitial lung disease (ILD) or Pneumonitis Events**

Interstitial lung disease (ILD) or Pneumonitis Events	Management
(management overview)	
Interstitial lung disease (ILD) / pneumonitis has been identified as an adverse drug reaction for abemaciclib. Adverse events reported included events such as interstitial lung disease, pneumonitis, obliterative bronchiolitis, organizing pneumonia, pulmonary fibrosis. The majority of events were Grade 1 or Grade 2 with serious cases and fatal events reported.
 
Patients should be asked to report any new or worsening pulmonary symptoms such as dyspnea, cough and fever; these symptoms should be investigated and treated as per local clinical practice and/or guidelines (including corticosteroids as appropriate). Investigations may include imaging such as high resolution computer tomography (HRCT), bronchoalveolar lavage (BAL), and biopsy as clinically indicated.

Grade 1, development of radiological or PFT changes suggestive of pneumonitis and have few or no symptoms	
 
Perform high-resolution CT scan (defined as slice thickness of 1 to 1.25mm and use of high special frequency algorithm).
 
If after initial workup, the patient does not meet CTCAE 5.0 criteria for grade <math>\geq 2</math> pneumonitis/ILD (symptomatic or needing medical intervention), treatment may be continued
 
The patient will be monitored closely with high-resolution CT scans and PFTs every 8 weeks until resolution of Grade 1 pneumonitis or until worsening to grade <math>\geq 2</math> pneumonitis/ILD at which time the treatment must be withheld per protocol.
 
Consider patient referral to pulmonary specialist.
 

Grade 2, 3 or 4	
 
Permanently discontinue abemaciclib and atezolizumab and contact Sponsor-Investigator.
 
Referral to pulmonary specialist is recommended with consideration of bronchoscopy or BAL.
 
Initiate treatment with 1-2 mg/kg/day oral prednisone or equivalent.
 
If event does not improve within 48 hours after initiating corticosteroids, consider adding an immunosuppressive agent.
 
If event resolves to Grade 1 or better, taper corticosteroids over <math>\geq 1</math> month.
 
Patients who develop <math>\geq</math> grade 2 pneumonitis/ILD must withdraw from further study treatment
 

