The investigator should consider the benefit–risk balance for a given patient prior to further administration of atezolizumab. In patients who have met the criteria for permanent discontinuation, resumption of atezolizumab may be considered if the patient is deriving benefit and has fully recovered from the immune-mediated event. The decision to re-challenge patients with atezolizumab should be based on investigator’s assessment of benefit–risk and documented by the investigator.

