**Table 5. Management Guidelines for Pulmonary Events, Including Pneumonitis**

Event	Management
Pulmonary Event, Grade 1	
 
Continue atezolizumab and monitor closely.
 
Re-evaluate on serial imaging.
 
Consider patient referral to pulmonary specialist.
 
For Grade 1 pneumonitis, consider withholding atezolizumab.
 

Pulmonary Event, Grade 2	
 
Withhold atezolizumab for up to 12 weeks after event onset.a
 
Refer patient to pulmonary and infectious disease specialists and consider bronchoscopy or BAL.
 
Initiate treatment with corticosteroids equivalent to 1–2 mg/kg/day oral prednisone.
 
If event resolves to Grade 1 or better, resume atezolizumab.b
 
If event does not resolve to Grade 1 or better while withholding atezolizumab, permanently discontinue atezolizumab.c
 
For recurrent events, or events with no improvement after 48–72 hours of corticosteroids, treat as a Grade 3 or 4 event.
 
•
 

Pulmonary Event, Grade 3 or 4	
 
Permanently discontinue abemaciclib and atezolizumab and contact Sponsor-Investigator.
 
Oral or IV broad-spectrum antibiotics should be administered in parallel to the immunosuppressive treatment.
 
Bronchoscopy or BAL is recommended.
 
Initiate treatment with corticosteroids equivalent to 1–2 mg/kg/day IV methylprednisolone.
 
If event does not improve within 48 hours after initiating corticosteroids, consider adding an immunosuppressive agent.
 
If event resolves to Grade 1 or better, taper corticosteroids over <math>\geq</math> 1 month.
 

BAL = bronchoscopic alveolar lavage.a Atezolizumab may be withheld for a longer period of time (i.e.,  $> 12$  weeks after event onset) to allow for corticosteroids (if initiated) to be reduced to the equivalent of  $\leq 10$  mg/day oral prednisone. The acceptable length of the extended period of time must be based on an assessment of benefit–risk by the investigator and in alignment with the protocol requirements for the duration of treatment and documented by the investigator.

b If corticosteroids have been initiated, they must be tapered over  $\geq$  1 month to the equivalent of  $\leq 10$  mg/day oral prednisone before atezolizumab can be resumed.

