c Resumption of atezolizumab may be considered in patients who are deriving benefit and have fully recovered from the immune-mediated event. The decision to re–challenge patients with atezolizumab should be based on investigator's assessment of benefit–risk and documented by the investigator (or appropriate delegate).

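### For patients on atezolizumab, Table 5 directs resumption after grade 2 pneumonitis resolves, while Table 27 footnote 8 and Table 21 require stopping, and nothing says which rule prevails

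*Combined protocol and SAP*

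**What the plan says.** **Section 6.1, Table 5** covers pulmonary events and names pneumonitis in its title. In the grade 2 row, atezolizumab is withheld for up to 12 weeks and corticosteroids are started. Then: "If event resolves to Grade 1 or better, resume atezolizumab". If the event does not resolve, atezolizumab is permanently discontinued, but footnote c qualifies that: "Resumption of atezolizumab may be considered in patients who are deriving benefit and have fully recovered from the immune-mediated event".

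**Section 6.2, Table 21** gives one rule for grades 2, 3 and 4 pneumonitis/ILD: "Permanently discontinue abemaciclib and atezolizumab and contact Sponsor-Investigator". It closes by saying that a patient who develops at least "grade 2 pneumonitis/ILD must withdraw from further study treatment".

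**Section 10, Table 27 footnote 8**, attached to the pulmonary function tests, says that a patient who reaches grade 2 or higher pneumonitis/ILD must come off trial therapy. It has no limit by drug, regimen or arm.

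The opening of section 6 calls its dose delays and modifications requirements. It orders adjustment by whichever system shows the worst toxicity, but gives no order of precedence between its tables.

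**The concern.** The same event at the same grade has two outcomes depending on which page the site opens. An investigator who follows Table 5 to the letter re-doses a patient whom footnote 8 says must be discontinued, and so commits a deviation by following the protocol.

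The event is serious. Table 21 notes that fatal ILD/pneumonitis cases have been reported with abemaciclib. The Arm C atezolizumab patients are also the only ones for whom the exclusion for prior thoracic radiation is waived (section 3.3.18), and section 2.3.3 cites a pooled analysis suggesting more pneumonitis on checkpoint inhibitors in patients who had radiation therapy.

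**Working it through.** No power, alpha or sample size figure is involved, so the check is a comparison of texts followed by a head count.

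**1. The rules for grade 2 pneumonitis, side by side**

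| Text | Action | Force | Reach |
|---|---|---|---|
| Table 5, grade 2 row | Hold, then resume at grade 1 or better | Directive | Patients on atezolizumab |
| Table 5, footnote c | Re-challenge after a non-resolving event | Permissive | Same |
| Table 27, footnote 8 | Discontinue trial therapy | Mandatory | Any patient; no regimen limit |
| Table 21, grade 2-4 row | Permanently discontinue both drugs; withdraw | Mandatory | Names atezolizumab, but sits under abemaciclib management |

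**2. Can Table 5's grade 2 row be read as leaving pneumonitis out?** No. The title includes it. The grade 1 row gives pneumonitis its own instruction ("For Grade 1 pneumonitis, consider withholding atezolizumab"), so the authors separated it where they wished to. The grade 2 row makes no such exception.

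**3. Can footnote 8 be read as applying only to abemaciclib patients?** Not from its words. The pulmonary function tests are scheduled without an arm restriction. Footnote 6 in the same list is expressly limited to atezolizumab-containing regimens, so limits were written where they were meant.

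**4. Which texts collide for which patients?** For atezolizumab monotherapy, mainly Table 5 against footnote 8. For combination patients, Table 5 against both footnote 8 and Table 21.

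**5. Does the section 6 rule on the worst-affected system settle it?** No. There is one system, one event and one grade.

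**6. How many patients?** From the synopsis and section 1.1:
- Total: 27 (Arm A) + 8 (Arm B) + 21 (Arm C) = 56, with Arm C = 5 atezolizumab + 16 abemaciclib.
- Atezolizumab monotherapy, planned: 5/56 = 8.9%.
- Arm B, treated: 8/56 = 14.3%. The number still on treatment is not given. If the two grade 5 sepsis events were in two different patients, it lies between 0 and 8 − 2 = 6.
- Abemaciclib alone: 27 + 16 = 43, and 43/56 = 76.8%. Table 5's resume instruction does not concern them.

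**7. How often might it arise?** The documents give no rate of grade 2 pneumonitis for this setting. Assuming a risk of 1% to 5% per patient, the expected number among the five is 5 × 0.01 = 0.05 to 5 × 0.05 = 0.25. The chance of at least one case is 1 − 0.99^5 = 5% to 1 − 0.95^5 = 23%.

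**The case against.** The strongest reply is to read by drug: Table 5 governs atezolizumab and Table 21 governs abemaciclib. Table 21 stands under abemaciclib toxicity management, opens with pneumonitis as a reaction to abemaciclib, and its order to stop both drugs most naturally describes a patient taking both. This has weight, and a reader who infers that Table 21 binds the five monotherapy patients as firmly as combination patients goes further than its placement allows. It does not remove the conflict, because footnote 8 stands outside section 6.2 and carries no such limit.

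Two other readings would enlarge the point, and the documents do not support them.
- A reader might count the general section 6.1 text as further direct contradictions: "In patients who have met the criteria for permanent discontinuation, resumption of atezolizumab may be considered if the patient is deriving benefit", and the similar permission after a hold of more than 12 weeks. Both are generic and permissive, and the list before the first is introduced as covering events not dealt with in the later subsections, whereas pneumonitis is dealt with. Only Table 5's grade 2 row directs re-treatment.
- A reader might see a further conflict in Table 21's grade 1 row, where worsening leads to grade 2 or higher "pneumonitis/ILD at which time the treatment must be withheld per protocol". The row directly below says what then happens: permanent discontinuation, with no hold-and-resume option.

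It is also fair to say that little may come of this in practice. Arm B is closed and the remaining group is small. A site can always stop: section 5.4 lets the treating investigator end therapy, and section 6.1 asks the investigator to weigh the benefit–risk "balance for a given patient prior to further administration of atezolizumab". Section 6 also invites questions to the sponsor's team. This limits the size of the point, but it does not tell a site which of two required actions is correct.

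Finally, the sponsor did set different limits for atezolizumab monotherapy elsewhere (thoracic radiation in 3.3.18, AST/ALT in 3.1.9), so hold-and-resume for that group could be intended. That bears on which rule to choose, not on whether one must be chosen.

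**Conclusion.** The inconsistency is real and should be corrected. One directive row (Table 5, grade 2), with a permissive footnote c, stands against two mandatory texts, and no precedence is stated. The planned group is five Arm C patients; any Arm B patient still on treatment adds to it, by a number the documents leave open. Initial care at grade 2 is essentially the same in both tables, so the conflict concerns re-treatment only. The exposure runs one way: resuming under Table 5 breaches footnote 8, while withdrawing the patient is supported by other text.

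This is an inconsistency in safety conduct. It has no effect on sample size, power or the efficacy analysis. The conclusion rests on taking footnote 8 at its unrestricted wording and Table 5 at its title. No incidence is claimed beyond the assumed range above.

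**What to change.** State one rule.

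**Option 1, matching the two mandatory texts.** Add to the Table 5 grade 2 row: *For grade 2 pneumonitis/ILD, permanently discontinue study treatment per Table 21 and Table 27 footnote 8; footnote c and the general re-challenge text do not apply.* Keep hold-and-resume for other grade 2 pulmonary events. The downside is that a few atezolizumab patients who are benefiting lose the option to resume.

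**Option 2, if the sponsor intends hold-and-resume on atezolizumab alone.** Limit the Table 21 grade 2-4 row and footnote 8 explicitly to abemaciclib-containing regimens. If any combination patient is still on treatment, the Table 5 row must also say that resumption applies to atezolizumab alone; otherwise the clash remains for that patient. The downside is that re-treatment stays possible in patients who may have had thoracic radiation.

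Either option is a short wording amendment with a notice to sites. Neither changes the design, sample size or analysis.
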